1 INTRODUCTION

1.1 Background

Nearly all (> 90%) dialysis patients in the United States are treated with erythropoiesis stimulating agents (ESAs) and supplemental iron for management of chronic anemia and transfusion avoidance. However, the requirement for supra-physiologic ESA doses to maintain clinical guideline and FDA-specified target hemoglobin levels suggests some degree of erythropoietic inefficiency in these “hyporesponsive” patients (MacDougall 2005, Sun 2012). In the healthy state, serum erythropoietin levels are approximately 12-15 U/L. After a 2-unit phlebotomy and decline in hemoglobin from 15 g/dL to 12 g/dL, erythropoietin levels increase over 10-fold to approximately 200 U/L transiently. In contrast, a moderate-for-dialysis patient intravenous dose of erythropoietin of 3000 U results in a peak erythropoietin level of approximately 1000 U/L, levels not achieved with native erythropoietin production until the hemoglobin levels reach 5 g/dL (Fishbane 2007).

Erythropoiesis stimulating agent trials randomizing patients to higher vs. lower hemoglobin targets have shown an increase in cardiovascular events among those treated to higher hemoglobin targets in both dialysis-dependent and non-dialysis dependent chronic kidney disease patients (Besarab 1998 and Singh 2006). Analyses of these trials and others have shown that patients at greatest risk for cardiovascular events were those randomized to the higher hemoglobin target who failed to achieve said target (i.e. hyporesponders) and, per protocol, were treated with higher ESA doses (Fishbane 2007 and Kilpatrick 2008). A number of potential, non-mutually exclusive mechanisms have been suggested to explain these observations (e.g., potential direct toxic effects of non-biologic ESAs and/or iron, increased platelet activity, hyperviscosity, and endothelial damage) and all of these mechanisms are superimposed upon individual ESA responsiveness. ESA hyporesponsiveness is also a manifestation of the malnutrition-inflammation complex in which inflammation is associated with reductions in pre-albumin and albumin (Kalantar-Zadeh 2003) and treatment of inflammation has been shown to improve nutritional markers (Hung 2011).

Patients with the most marked ESA hyporesponsiveness are characterized by lower hemoglobin levels, lower transferrin saturation levels, and normal or high ferritin levels (Kharagjitsingh 2005). Together, these parameters point to a functional blockade in release of iron for erythropoiesis from bodily stores. One important mechanism for this blockade is inflammation-induced expression of the “master iron regulator” hepcidin, a protein which prohibits cellular iron transport via degradation of ferroportin, the only known iron export channel in humans (Hentze et al 2004, Hentze et al 2010 and Sun 2012). Use of high doses of intravenous iron can partially overcome this blockade, but higher doses (> 400 mg/month) are associated with higher cardiovascular mortality and all cause mortality in the context of inflammation (Kalantar-Zadeh 2005). Current anemia treatments do not reduce inflammation and, therefore, fail to address an important mechanism of anemia in this population.

These observations form the basis for targeting inflammation as a means to treat anemia in the dialysis population. Inhibiting inflammation and thereby improving functional iron

deficiency would be expected to reduce the required ESA and iron supplementation at any level of targeted hemoglobin and potentially alleviate associated iatrogenic complications.

1.2 Description of COR-001

Additional information about the mechanism and structure of COR-001 can be found in the COR-001 [Investigator's Brochure](#).

[figure not shown]
COR-001 is a human IgG1, kappa antibody directed against interleukin-6 (IL-6), containing a "YTE" mutation in its Fc region which affords the potential for extended half life. COR-001 is being developed for the treatment of anemia in genotype positive patients with chronic kidney disease on hemodialysis.

Alleviation of inflammatory anemia with anti-IL-6 therapy comes from published work regarding the use of said therapy in humans in non-renal inflammatory conditions. Tocilizumab (Roche) and clazakizumab (Alder Biopharmaceuticals) have both shown ability to raise hemoglobin in rheumatoid arthritis, Castleman's disease and advanced malignancy ([Song 2010](#), [Song et al 2013](#), [Bayliss 2011](#)). By example, the administration of tocilizumab (anti-IL-6 receptor antibody) reverses signs of inflammation, improves iron availability, and increases hemoglobin in Castleman's patients.

Although anti-IL-6 therapies have not been tested in dialysis patients to date, published and Sponsor's unpublished data in a large prevalent dialysis population documents a correlation between serum IL-6 levels and the degree of ESA hypo-responsiveness (i.e., erythropoietin dose requirement divided by achieved serum hemoglobin) ([Won 2012](#) and see [Section 2](#) of the COR-001 Investigator's Brochure).

However, the influence of IL-6 is not universal, and appears over-represented in a specific, genotypically defined dialysis subpopulation. Based on non-clinical study and retrospective review of dialysis populations (Sponsor's unpublished data), it appears a genotypic variation in the iron-control system of mammalian cells can render tissues more or less susceptible to IL-6 based inflammation, and dictate the influence of this inflammation on clinical outcomes (see [Figure 1](#) and [Section 2](#) of the COR-001 Investigator's Brochure).

Figure 1 A model for the influence of genetic variation on IL-6 mediated cellular iron handling

BMPR = BMP receptor
IL-6R = IL-6 receptor
HAMP =hepcidin gene
FPN = ferroportin
Fe = iron

1.3 Summary of Relevant Nonclinical Experience with COR-001

1.3.1 *Non-Clinical Pharmacology*

In vitro studies were conducted to determine the affinity, potency and specificity of COR-001. These studies confirm COR-001 is highly (sub-pico-molar) potent and outcompetes cell bound or soluble IL-6 receptors, thus effectively preventing circulating IL-6 from binding to its receptors and eliciting effects via classical or trans-signaling. A preclinical proof of concept study in a cardio-renal rodent model was conducted to expand on published data and the rationale for the intended indication. Further preclinical studies elucidated the direct and indirect mechanisms of IL-6 mediated inflammatory cardiac injury.

1.3.2 *Pharmacokinetics in animals*

Cynomolgus monkey was selected as the pharmacologically relevant animal model to characterize the pharmacokinetics (PK) and pharmacodynamics (PD) of COR-001 and conduct nonclinical safety assessment studies. One single-dose non-GLP study and one multiple-dose GLP study was conducted.

The elimination half-life of COR-001 was extended by approximately 3-fold and the clearance was reduced by approximately 4-fold compared to the parent molecule lacking the YTE Fc region mutations. The average half-life of COR-001 ranged from 27.2 to 28.8 days and clearance from 2.76 to 3.88 mL/day/kg.

1.3.3 *Non-Clinical Toxicology and Safety*

The nonclinical toxicology data for COR-001 include two studies in cynomolgus monkeys: a non-GLP single IV or SC dose PK and pharmacodynamics study, and a GLP repeat IV or SC administration toxicology study (every other week administration for 13-weeks with a 16-week recovery). In the non-GLP single-dose study, although there was no control group comparator, there were no adverse findings attributed to single COR-001 administration of 5 mg/kg IV or 50 mg/kg SC injections, the highest doses tested.

In the GLP repeat-dose study, the NOAEL was 100 mg/kg for animals dosed IV and 50 mg/kg for animals dosed SC, the highest doses tested. In addition, GLP tissue cross-reactivity studies in a full panel of human and cynomolgus monkey tissues showed staining judged as expected.

1.4 Summary of Relevant Clinical Experience

1.4.1 *Phase 1 Study of COR-001 in Rheumatoid Arthritis Patients*

The clinical program to date consists of a single Phase 1, double blind, placebo controlled single ascending dose study in rheumatoid arthritis patients (Study D4430C00001) conducted by MedImmune from 21 May 2012 to 25 February 2014. Dose escalation was to begin at 30 mg, with provisional doses of 90, 270, and 600 mg thereafter. After 4 patients were enrolled (3 receiving COR-001 30 mg IV (single dose) and 1 receiving placebo), the study was terminated due to difficulties with recruitment.

2 STUDY OBJECTIVES

In a genotype positive population of maintenance hemodialysis patients with elevated IL-6 levels, the objectives are as follows:

Primary objective:

- To evaluate the safety of multiple doses of COR-001

Secondary objectives:

- To model the relationship of COR-001 pharmacokinetics and primary pharmacodynamics as assessed by free and total serum IL-6, high-sensitivity C-reactive protein (hsCRP) and serum amyloid A (SAA)
- To evaluate the secondary pharmacodynamic effects of COR-001 as assessed by:
 - Systemic iron availability (transferrin saturation, TSAT, reticulocyte hemoglobin, CHr) and reticulocyte count
 - Systemic iron stores (serum ferritin and supplemental iron dose requirements)
 - Erythropoiesis stimulating agent resistance index (ERI)
 - Malnutrition-inflammation (pre-albumin, albumin)
 - Serum cardiac biomarkers (Troponin T and N-terminal pro-B-natriuretic peptide, NT-proBNP)
 - Left ventricular mass index (LVMI) by non-contrast MRI
 - Physical function by handgrip strength and symptoms of fatigue
- To investigate the immunogenicity of COR-001

3 INVESTIGATIONAL PLAN

3.1 Overall Study Design and Plan: Description

This is a randomized, double-blind, placebo-controlled trial designed to evaluate the safety, pharmacokinetics, and pharmacodynamic effects of multiple doses of COR-001 or placebo administered to sequential cohorts of hemodialysis patients.

Ten hemodialysis patients will be randomized to COR-001 or placebo within each dosing cohort. When a higher dose than studied in a prior cohort is being initiated, the first 2 (sentinel) patients in that cohort will be randomized 1:1 to COR-001 or placebo; the remaining patients will be randomized at least 48 hours later in a 7:1 ratio of COR-001 to placebo.

Prior to dose escalation (i.e., higher total dose than studied in the preceding cohorts), there will be a formal safety review by the Safety Review Committee (SRC), which will include at least one nephrologist. The SRC will specifically determine whether the maximum tolerated dose (MTD) has been exceeded based on protocol-defined dose-limiting toxicities occurring through Study Day 21 in the 8 actively-treated patients in the current cohort (see [Figure 2](#)). In addition, PK and PD results will be reviewed to assess the appropriateness of the next planned dose and to guide revision of the next dose to be evaluated, if necessary. The planned doses are shown in [Table 2](#). These doses may be adjusted based on accruing data; however, the maximum dose to be studied will not exceed the planned total dose in Cohort 4 (60 mg every 14 days [6 doses]).

A single interim analysis (described in [Section 11.5](#)) is planned to enable future program planning.

Patients will undergo a Screening Period during which the ESA dose and parenteral iron doses must have been stable, as defined in the inclusion and exclusion criteria. Patients randomized to both COR-001 and placebo will be continued on ESA and parenteral iron (if being given).

Patients meeting the entry criteria will be randomized on Day 1 (a dialysis day), following which they will receive the first dose of Study Drug during dialysis. Additional visits will follow the schedule of events ([Appendix A](#)). All subsequent Study Drug infusions will also be administered during dialysis and study visits will coincide with regularly scheduled dialysis treatments. Patients dropping out (i.e., prematurely discontinuing Study Drug treatment) for reasons unrelated to safety may be replaced.

Following the 12-week Treatment Period, patients will be followed for an additional 12 weeks for safety in the Safety Follow-Up Period. The patient's will have completed their primary study participation at Week 24 (end of the Safety Follow-Up Period). Sparse blood samples will be additionally collected on Week 35 for anti-drug antibodies, pharmacokinetics, and IL-6 measurements as part of an Extended Follow-Up Period.

3.1.1 *Pharmacokinetic and PK-PD Modeling*

- Serum COR-001 concentrations will be subjected to PK modeling and secondary PK parameters such as maximum serum drug concentrations (C_{max}), area under the serum drug concentration-time curve (AUC) and terminal elimination half-life ($t_{1/2}$) will be calculated.
- The free (unbound to COR-001) and total (free + bound) IL-6 AUC will be described
- The change in serum concentration of COR-001 from pre-dialysis to post-dialysis will be described
- The relationship between COR-001 pharmacokinetics and primary pharmacodynamic endpoints, specifically free and total serum IL-6, high-sensitivity C-reactive protein (hsCRP) and serum amyloid A (SAA) will be described.

3.1.2 *Safety Endpoints*

Primary

- Characterization of the MTD or to establish that the highest dose examined did not exceed the MTD

Secondary

- Description of the frequency of DLTs (defined in [Section 4.4](#)) by treatment group and dose
- Description of the frequency of the events of interest by treatment group and dose (defined in [Section 9.3](#))
- Description of additional safety assessments by treatment group and dose: adverse events, vital signs, ECG, clinical laboratory, and anti-drug antibodies (binding and neutralizing)

3.1.3 *Pharmacodynamic Endpoints*

Data from COR-001-treated patients from Cohorts not exceeding the MTD will be pooled and data from all placebo patients will be pooled for the pharmacodynamic endpoint analyses.

Primary

- Change from baseline (mean of Screening and Day 1) in the SAA and hsCRP to Week 4 between treatment groups

Secondary

- Mean differences between placebo and COR-001-treated patients will be determined for the following parameters:
- Change from baseline (mean of Screening and Day 1 values) in TSAT to Week 4
- Change from baseline (mean of Screening and Day 1 values) in the CHr to Week 4
- Change from baseline (mean of Screening and Day 1 values) in hsCRP to the mean of Weeks 10 – 12
- Change from baseline (mean of Screening and Day 1 values) in SAA to the mean of Weeks 10 – 12
- Change from baseline (mean of Screening and Day 1 values) in serum pre-albumin to the mean of Weeks 10 – 12 and albumin to Week 12
- Change from baseline (weekly mean of Screening) in ERI to Week 4 among patients
- Change from baseline (weekly mean of Screening) in ERI to the mean of Weeks 8 – 12

[figure not shown]
Exploratory

- Description of the systemic iron availability (TSAT, absolute reticulocyte count, hemoglobin, CHr) over time
- Description of markers of malnutrition-inflammation (pre-albumin and albumin) over time
- Description of systemic iron stores (serum ferritin, hepatic and splenic iron content by MRI, and supplemental iron dose requirements) over time
- Description of ERI change from baseline (weekly mean during the Screening Period) through Week 24
- Description of changes ESA and parenteral iron dose requirements from baseline (weekly mean during the Screening Period) to Evaluation Period (Weeks 8 – 12) and through Week 24
- Description of changes in LV mass index from Screening to Week 12

- Description of changes in pre-dialysis, post-dialysis, and delta-serum Troponin and NT-proBNP (defined as the difference between the pre- and post-dialysis troponin) from baseline (mean of Screening) to Weeks 10 – 11
- Description of handgrip strength from baseline (during Screening) to Week 12
- Description of the FACIT fatigue score from baseline (during Screening) to Week 12

3.2 Study Schematic

Figure 2 Dose Escalation Schematic

- ¹ If the MTD is not exceeded, dose escalation may continue.
- ² If the MTD is exceeded, a lower dose, including previously studied dose, may be selected.

The MTD assessment will be based on safety data from Weeks 1 to 3. If more than 2 of 8 active patients in a cohort experience a DLT, the MTD will be considered to have been exceeded.

The planned doses shown here may be adjusted based on accruing PK, PD, and safety data. The highest dose that will be studied is a cumulative dose of 360 mg. Expansion cohorts to further evaluate doses below the dose that exceeded the MTD may be initiated at any time.

The randomization ratio within each cohort will be 8:2 (COR-001 to placebo).

3.3 Blinding and Randomization

3.3.1 Randomization

Randomized treatments will be assigned via an interactive web-response system (IWRS). Ten hemodialysis patients will be randomized to COR-001 or placebo within each dosing cohort. When a higher dose than studied in a prior cohort is being initiated, the first 2 (sentinel) patients in that cohort (randomized 1:1 to COR-001 or placebo) will be randomized first and the remaining patients will be randomized at least 48 hours later, in a 7:1 ratio of COR-001 to placebo. For cohorts in which doses are less than the dose that exceeded the MTD (determined from earlier cohorts), randomization of all 10 patients will proceed in parallel to achieve an 8:2 ratio of COR-001 to placebo.

3.3.2 Blinding

This study is double-blind. The patients, investigators, site personnel (not including site personnel responsible for drug versus placebo preparation), site monitors and Sponsor clinical operational personnel will be blinded to the treatment assignment. The Sponsor representative(s) on the SRC will become unblinded for the safety reviews of each cohort in order to select doses for the next cohort. The SRC will be unblinded. In addition, contract research organization (CRO) personnel analyzing the PK samples and performing the PK, target engagement, and analysis of PK/pharmacodynamic relationships and those responsible for interactive web-response system (IWRS) will have access to the randomization list. The randomization list will be generated by a CRO statistician not otherwise involved in the study or the SRC unblinded statistician.

3.3.3 Unblinding

In case of a medical emergency or medical situation in which the treatment assignment is necessary for proper patient management, the Investigator may obtain the treatment assignment from the IWRS. The Investigator should make every reasonable attempt to contact the Medical Monitor before unblinding a patient. In all cases, the Investigator must submit a written report, including all pertinent details, to the Medical Monitor within 24 hours of the unblinding.

3.4 Duration of the Study

The total study duration for an individual patient will be approximately 9 months, excluding the Screening Period. The study periods are as follows:

- Initial Screening Period: Up to 2 weeks [Days -28 to -15]
 - Starts with the first date that Initial Screening procedures were performed. The first procedure also defines the Initial Screening visit date.
- Full Screening Period: up to 2 weeks [Days -14 through Day -1]
 - Starts with the date of the Week -2 Visit

- Treatment Period: 12 weeks [Week 1, Day 1 through Week 12]
 - Safety Follow-Up Period: 12 weeks [Weeks 13 through 24]
- Extended Follow-Up Period: 10 weeks [Weeks 25 through 35]

3.5 Discussion of Study Design, Including Choice of Control Arm

The study is a randomized (within cohort), double-blind, placebo-controlled trial. Randomization and double-blinding are being used to minimize bias. The treatment duration (12 weeks) was chosen as the shortest duration needed to evaluate the pharmacodynamic effect of said doses on the proposed inflammatory, hematologic and cardiovascular endpoints. Sample size calculations were performed for several pharmacodynamics endpoints and these are presented in [Section 11.1](#).

3.5.1 Study Population and Control Arm

Because the Study Drug is being administered in addition to current treatments for anemia, a placebo-control is justifiable. As there are no currently approved treatments that improve functional iron deficiency, there are no options for an active comparator.

The study is being conducted in the target population because the pharmacodynamic endpoints (inflammation, functional iron deficiency, and left ventricular hypertrophy and strain) cannot be evaluated in healthy volunteers.

Further, as human pharmacokinetic data to date are available only from a non-chronic kidney disease population, it is one aim of the study to obtain PK data in the hemodialysis population.

3.5.2 Rationale for Dosing and Length of Safety Evaluation

Inhibition of free IL-6 greater than 90% is needed to achieve biologic effect, because growth factors and soluble cytokines in general are able to elicit signaling with receptor occupancies of less than 10%. A basic logarithmic dose escalation scheme was used after modeling of IL-6 binding and the PK-PD (hsCRP) relationship from the concluded Phase 1 trial in RA patients (Study D4430C00001). Based on the clearance of COR-001 (dictated by the “YTE” Fc mutation), the duration of safety monitoring for 24 weeks following the last dose and extended follow-up for PK, IL-6, and antibody testing to 35 weeks is planned.

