	
limiting toxicities occurring through Study Day 21 in the 8 actively treated patients in the current cohort (see Figure 2). In addition, pharmacokinetic and pharmacodynamic results will be reviewed to assess the appropriateness of the next planned dose and to guide revision of the next dose to be evaluated, if necessary.
 
Patients will undergo an up to 4-week Screening Period during which the ESA dose and parenteral iron doses must have been stable, as defined in the inclusion and exclusion criteria. All patients randomized will be continued on ESA and parenteral iron (if being given).
 
Patients meeting the entry criteria will generally be randomized on Day 1. The first dose of Study Drug will be administered during dialysis. Administration of the first dose of Study Drug will define Study Day 1. Additional visits will follow the schedule of events (see Appendix A: Schedule of Events). All subsequent Study Drug infusions will also be administered during dialysis and study visits will coincide with regularly scheduled dialysis treatments. Patients dropping out (i.e., prematurely discontinuing Study Drug treatment) for reasons unrelated to safety may be replaced in order to maintain the randomization ratio within each cohort.
 
Following the 12-week Treatment Period, patients will be followed for an additional 12 weeks for safety in the Safety Follow-Up Period. Patients will have completed their primary study participation at Week 24 (end of the Safety Follow-Up Period). Limited blood sampling will occur on Week 35 for anti-drug antibodies, pharmacokinetics, and IL-6 measurements as part of an Extended Follow-Up Period.

Study Periods:
	
The total study duration for an individual patient will be approximately 9 months, excluding the Screening Period.
 
Initial Screening Period: up to 2 weeks [Days -28 to -15]
 
 •Starts with the first date that Initial Screening procedures were performed. The first procedure also defines the initial screening visit date. 
Full Screening Period: up to 2 weeks [Days -14 through Day -1]
 
 •Starts with the date of the Week -2 Visit 
Treatment Period: 12 weeks [Week 1, Day 1 through Week 12]
 
Safety Follow-Up Period: 12 weeks [Weeks 13 through 24]
 
Extended Follow-Up Period: 10 weeks [Weeks 25 through 35]

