5.6 Extended Follow-Up Procedures (Study Week 35)

5.6.1 Week 35

- Obtain Central Laboratory blood samples within 15 minutes prior to the start of dialysis

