9.6 Adverse Event Reporting

The AE reporting period starts with the signing of the Long ICF and continues through the Week 24 study visit, other than for AEs believed to be related to study procedures, which should be recorded starting with the signing of the Short ICF. Patients in this study who experience a drug-related AE or SAE will be followed until the AE or SAE is resolved or stabilizes per the Investigator's judgment, even if this occurs after the final study visit. All AEs spontaneously reported by the patient and/or in response to an open question from study personnel or revealed by observation, physical examination, or other diagnostic procedures will be recorded and reported on the appropriate CRF. When a unifying diagnosis has been made that accounts for several possible signs and/or symptoms, the unifying diagnosis should be selected as the AE term. For example, the combination of general malaise, mild fever, headache, and rhinitis should be described as "upper respiratory syndrome" if this diagnosis has been made, rather than reporting the individual symptoms as separate events.

If any laboratory test is newly abnormal during the course of the study, it will be followed at the discretion of the Investigator. Abnormalities of laboratory tests which are, in the opinion of the Investigator, clinically significantly worse compared to prior to the signing of the Long ICF, or for which a medical intervention is initiated, should be reported as AEs on the AE CRF.

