9.7 Reporting of Serious Adverse Events and Adverse Events of Special Interest

The SAE reporting period is the same as the AE reporting period. All SAEs that occur during the reporting period and regardless of causality, must be reported by the Investigator to [REDACTED] by completing the SAE Form in the electronic data capture (EDC) system. Any pertinent source documents should also be submitted as soon as they are available. Do not withhold submission of an SAE even if complete information about the event is not available at the time of the initial report. Follow-up information on the SAE should be sent promptly by the Investigator when any additional relevant information about the event becomes known to the Investigator, or as requested by [REDACTED] or Corvidia Therapeutics.

SAE and Pregnancy Reporting Contact Information

Hypersensitivity reactions (see [Section 8.2](#)) occurring during the Study Drug infusion and anaphylaxis occurring anytime during Weeks 1 – 24 of the study should be reported as adverse or serious adverse events within the EDC AE and SAE CRFs within 24 hours of the site's awareness of the event. A supplemental CRF will also be completed for such events. Please submit as much information as is available with the initial report.

Corvidia Therapeutics will immediately notify the Investigator about important safety or toxicology information as it becomes available. It is the responsibility of the Investigator to promptly notify the IRB/ IEC about new and relevant safety information regarding the Study Drug, including serious adverse drug reactions involving risk to human subjects, in accordance with the applicable policies. An unexpected event is one that is not listed by nature or severity in the [Investigator's Brochure](#).

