Schedule of Events for the Safety Follow-Up and Extended Follow-Up Periods

Study Week	Safety Follow-Up Period					Extended F/U
	14	16	18	20	24/ET-2	35
Visit Window	± 3	± 3	± 3	± 3	± 3	± 7
Study Day	92	106	120	134	162	239
ESA and iron dosing per Appendix C						
Lab Panel 1 [CHEM]					X[a]	
Albumin	X		X			
Lab Panel 2 [LIP], Lp(a), serum pregnancy [1]					X[a]	
Lab Panel 3 [INFL1]	X[a]		X[a]		X[a]	
hsCRP	X[a]		X[a]		X[a]	X[a]
Pre-Albumin					X[a]	
Lab Panel 4 [SPRBC]	X[a]	X[a]	X[a]	X[a]	X[a]	
Lab Panel 5 [HEME]	X[a]	X[a]	X[a]	X[a]	X[a]	
Lab Panel 6 [IRON]	X[a]	X[a]	X[a]	X[a]	X[a]	
Lab Panel 7 [PK]	X[a]		X[a]			X[a]
Lab Panel 10 [ADA]					X[a]	X[a]
Lab Panel 11 [INFL2]	X[a]		X[a]		X[a]	X[a]
Local Lab INR [2]	X[a]	X[a]	X[a]	X[a]	X[a]	
12-lead ECG (pre-dialysis)			X		X	
Limited Physical Examination [3]			X		X	
Vital Signs (pre-dialysis) [4]	X	X	X	X	X	
Adverse Events	X					
Concomitant Medications	X					

[1] Serum pregnancy in women of childbearing potential only.

[2] Patients receiving warfarin only. May also be done using a point of care device.

[3] Limited physical exam to include skin, oropharynx, lungs, heart, abdomen, extremities (including feet), and any areas suggested by symptoms, with particular attention to signs of infection. May be performed by a physician-investigator or mid-level provider. Record abnormal findings in the source documents.

[4] Obtain blood pressure, heart rate, respiratory rate, and temperature: within 30 minutes prior to dialysis.

Every effort should be made to conduct the study visits on the same day of the week (e.g. on Wednesdays)

Laboratory test panels are defined in [Appendix D](#).

ET-2 = Early Termination Visit 2 (see [Section 5.8](#))

[a], [b], [c], [d] Please see [Footnote i](#)

Footnote i: Footnotes Common to All Schedule of Events' Tables

[a] Within 15 minutes prior to dialysis. Draw blood through either a peripheral needle stick or the arterial dialysis needle before connecting the arterial blood tubing or flushing the needle. Be sure that no saline or heparin is in the arterial needle or tubing prior to drawing the sample.

[b] Within 10 minutes after completing the infusion

If dialysis has ended, draw the sample after the machine has been turned off, either through a peripheral needle stick or from the arterial needle tubing prior to taking out the needle or arterial blood line/sample port.

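### Protocol 3.5.2 states 24 weeks of safety monitoring after the last dose, but AE collection ends 13 weeks after it, so new events in Weeks 24 to 35 have no collection requirement

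*Protocol*

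**What the plan says.** Protocol 3.5.2, the section on the length of safety evaluation, derives from the antibody's clearance "the duration of safety monitoring for 24 weeks following the last dose", with further PK, IL-6 and antibody sampling to 35 weeks.

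The operative sections all stop at study Week 24:

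- Synopsis and 3.1: after the 12-week Treatment Period, "patients will be followed for an additional 12 weeks for safety in the Safety Follow-Up Period".
- 9.6: "The AE reporting period starts with the signing of the Long ICF and continues through the Week 24 study visit".
- 9.7: "The SAE reporting period is the same as the AE reporting period". Its supplementary rule covers "anaphylaxis occurring anytime during Weeks 1 – 24 of the study".
- 4.3 and 5.8.1: chart-review follow-up for AEs after withdrawal of consent runs to Week 24.
- 5.7: AEs must be recorded at unscheduled visits that occur before Week 24.
- SAP 8.3: the treatment-emergent window closes when safety follow-up ends.

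For the later visit, the Synopsis says "Limited blood sampling will occur on Week 35 for anti-drug antibodies, pharmacokinetics, and IL-6 measurements". The whole Week 35 procedure in 5.6.1 is "Obtain Central Laboratory blood samples within 15 minutes prior to the start of dialysis". Appendix A gives the follow-up calendar, Weeks 14 to 35, as "Study Day 92 106 120 134 162 239".

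**The concern.** The rationale and the schedule give different lengths of post-dose safety monitoring. The rationale depends on a half-life-extended antibody clearing slowly, so a shorter window falls where the argument says monitoring is needed. Protocol 4.3 adds that the drug's effect is long-lasting and that monitoring after stopping is sensible. Section 3.7 names infection and neutropenia as risks of the class. Safety is the primary objective.

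If 24 weeks after the last dose was intended, a new infection between Weeks 24 and 35 need not be asked about or reported, and it would fall outside the SAP's treatment-emergent tables. If study Week 24 was intended, 3.5.2 overstates post-dose safety monitoring by a factor of 24/13 = 1.85.

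**Working it through.** **Calendar.** Inputs are dosing on Days 1, 15, 29, 43, 57 and 71, Week 12 at Day 78, Week 24 at Day 162 (±3) and Week 35 at Day 239 (±7), all from Appendix A. I tried to reproduce the stated 24 weeks from each plausible pair of dates:

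| Interval | Days | Weeks |
|---|---|---|
| Last dose to end of AE collection | 162 − 71 = 91 | 13.0 |
| Week 12 visit to end of AE collection | 162 − 78 = 84 | 12.0 |
| First dose to end of AE collection | 162 − 1 = 161 | 23.0 |
| Last dose to Week 35 visit | 239 − 71 = 168 | 24.0 |

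Only the last row gives 24 weeks after the last dose, and no AE collection is specified at that visit. The gap is 239 − 162 = 77 days, or 11.0 weeks.

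Visit windows do not close it. A last dose between Day 69 and Day 75 (two days early to the 96-hour late allowance) and a Week 24 visit between Day 159 and Day 165 give (159 − 75)/7 = 12.0 to (165 − 69)/7 = 13.7 weeks. Even a patient given only the Day 1 dose has at most (165 − 1)/7 = 23.4 weeks.

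The AE row of the follow-up schedule carries a single mark whose span cannot be read in the text. Sections 5.6.1 and 9.6 settle the matter without it.

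**Residual drug at Day 162.** Inputs are the 2 mg column of Protocol Table 1: peak 712 (first dose) and 1640 (last), trough 268 and 1042 ng/mL, cumulative AUC 167447 ng·day/mL. The other doses are proportional.

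1. *Trough accumulation, one compartment.* Solve (1 − r⁶)/(1 − r) = 1042/268 = 3.89, giving r = 0.822. Half-life = 14 × ln 2 / (−ln r) = 49.6 days. From the Day 85 trough, 77 days of decay: 1042 × 2^(−77/49.6) = 355 ng/mL, 21.7% of the last peak.
2. *Peak accumulation, one compartment.* Solve (1 − r⁵)/(1 − r) = (1640 − 712)/268 = 3.46, giving r = 0.815 and a half-life of 47.5 days. Day 162: 339 ng/mL, 20.6% of the last peak.
3. *Two compartments, fitted to all five values.* Per-dose concentration 436·e^(−0.189t) + 275·e^(−0.0108t), terminal half-life about 64 days. All five inputs are reproduced within 0.1%. Day 162: 440 ng/mL, 26.8% of the last peak. Day 239: 192 ng/mL, 11.7%.
4. *Monkey half-life, 27.2 to 28.8 days (Protocol 1.3.2).* Day 162: 146 to 163 ng/mL, 8.9 to 10.0% of the last peak. This fits Table 1 poorly. At 28.8 days, r = 2^(−14/28.8) = 0.714 and the six-dose trough ratio would be (1 − 0.714⁶)/(1 − 0.714) = 3.03, against 3.89 in the table.

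Methods 1 to 3 put the 2 mg concentration at Day 162 at 1.3 to 1.6 times the first-dose trough of 268 ng/mL. The monkey half-life puts it at 0.55 to 0.61 times.

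**The case against.** The strongest answer is that 3.5.2 contains a slip. Its sentence pairs 24 weeks with follow-up to 35 weeks. The 35 is plainly a study week, so the 24 may be one too, with the reference to the last dose added in error. Every operative section agrees on study Week 24, so no site or programmer would be misled. This stands as a plausible reading, but so does the other one, because Day 239 is exactly 24 weeks after Day 71. The documents do not settle the intent, and under either reading 3.5.2 and the schedule disagree.

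Three stronger readings might be inferred, and the documents do not support them.

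- *That late safety events in general go unrecorded.* Drug-related AEs and SAEs already reported are followed until resolved or stable, even past the final visit (9.6). AE forms still open stay unlocked until Database Lock 3, after Week 35 (SAP 11). Late data that happen to be collected go into listings (Protocol 11.3.3, SAP 2.3). The gap concerns new-onset events after the Week 24 visit.
- *That the primary safety endpoint is compromised.* The MTD is judged on DLTs through Study Day 21. Nothing in Weeks 24 to 35 bears on it.
- *That active drug at Week 24 is established.* Table 1 holds mean simulated exposures from a model built on the rheumatoid arthritis study, in which three patients received one 30 mg dose. Section 3.5.1 says human PK data came only from patients without chronic kidney disease. The text available to me states no human half-life, though part of the clinical-experience section was not available. A single half-life or residual percentage would be over-precise.

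It is also fair to say that adding an AE question at Week 35 is an imperfect remedy. The limits are given with the fix.

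**Conclusion.** The inconsistency is real and rests on calendar arithmetic alone: 13.0 weeks of AE collection after the last dose (12.0 to 13.7 with windows), against 24 stated. The 11-week difference is a shortfall in collection only if 3.5.2 expresses the intended rule. Otherwise it is an error in the rationale. Either way the text needs correcting.

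The consequence is limited to new-onset events between the Week 24 and Week 35 visits. It matters because the protocol's own simulated exposures imply roughly 20 to 27% of the last-dose peak at Week 24. That range assumes Table 1 carries over to dialysis patients and that elimination is first-order. The monkey half-life would give about 9 to 10%.

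This should be fixed. It does not threaten the MTD determination.

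**What to change.** Reconcile 3.5.2 with Protocol 3.4, 5.6, 9.6, 9.7 and Appendix A and with SAP 8.3, by one of two routes. The choice is the sponsor's.

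1. **If 24 weeks after the last dose is intended:** record AEs, SAEs and concomitant medications at the existing Week 35 visit for patients still in follow-up, and extend the reporting period in 9.6 and 9.7 to match. In the SAP, keep the Week 1 to 24 treatment-emergent tables as they are. Summarise events with onset after Week 24 separately, with the number of patients asked at each dose. The separation matters because SAP 11 expects Cohorts 1 to 4 (2 mg and 6 mg) to have completed the study by Database Lock 1, while 20 mg began in Cohort 5. Simply lengthening the treatment-emergent window could give the higher dose longer ascertainment than the lower ones.
2. **If study Week 24 is intended:** correct 3.5.2 to 13 weeks after the last dose.

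Route 2 costs one sentence. Route 1 costs a few CRF pages at a visit patients already attend, plus protocol and SAP wording. It relies on up to 11 weeks of recall and cannot cover patients already past Week 35. The Week 35 sampling has no hematology panel, so an AE question alone will not detect asymptomatic cytopenias, and the report should say so.
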